**e. Reactogenicity:**

Reactogenicity events are AEs that are known to occur with this type of vaccine. The following Toxicity Grading Scales will be used to grade local and systemic (both quantitative and subjective) reactions:

**Table 4. Local Solicited Adverse Events**

Local Reaction	Mild (Grade 1)	Moderate (Grade 2)	Severe (Grade 3)
Pain	Subject is aware of pain but it does not interfere with daily activity and no pain medication is taken	Subject is aware of pain; there is interference with daily activity or it requires therapeutic measures	Subject is aware of pain and it prevents daily activity or requires a healthcare visit
Tenderness	The area immediately surrounding the injection site hurts only when touched and it does not interfere with daily activity	The area immediately surrounding the injection site hurts only when touched and it interferes with daily activity	The area immediately surrounding the injection site hurts when touched and it prevents daily activity
Swelling/Induration	Does not interfere with daily activity	Interferes with daily activity	Prevents daily activity
Erythema/Redness	0.5 to 2.5 cm	>2.5 cm to <5 cm	≥5 cm
Induration/Swelling	0.5 to 2.5 cm	>2.5 cm to <5 cm	≥5 cm

**Table 5. Systemic Solicited Adverse Events**

Systemic (Subjective)	Mild (Grade 1)	Moderate (Grade 2)	Severe (Grade 3)
Fatigue/Malaise	No interference with activity	Some interference with activity	Incapacitating, prevents daily activity, may necessitate medical care or absenteeism
Headache	No interference with activity	Some interference with activity	Incapacitating, prevents daily activity, may necessitate medical care or absenteeism
Nausea	No interference with activity	Some interference with activity	Incapacitating, prevents daily activity, may necessitate medical care or absenteeism
Body ache/myalgia (not at injection site)	Less active than normal without interference with	Less active than normal with interference with	Incapacitating, prevents daily activity, may necessitate medical care or absenteeism

**Comparison of High vs. Standard Dose Flu Vaccine in Pediatric Stem Cell Transplant Recipients****DMID Protocol Number 16-0117****Protocol Version 8.0**

Date: 9/12/2019

	essential daily tasks (e.g. eating, sleeping)	essential daily tasks (e.g. eating, sleeping)	
General activity level	Less active than normal without interference with essential daily tasks (e.g. eating, sleeping)	Less active than normal with interference with essential daily tasks (e.g. eating, sleeping)	Incapacitating, prevents daily activity, may necessitate medical care or absenteeism
Vomiting	1-2 times a day	3-4 times a day	>4 times a day
Systemic (Quantitative)	Mild (Grade 1)	Moderate (Grade 2)	Severe (Grade 3)
Fever (°C) – ORAL	$\geq 38.0 - < 38.3$ $\geq 100.4 < 101^{\circ} F$	$\geq 38.3 - < 39$ $\geq 101 - < 102^{\circ} F$	$\geq 39$ $\geq 102^{\circ} F$

**f. Serious Adverse Event:**

An SAE is defined as an AE meeting one of the following conditions:

- Results in death during the period of protocol defined surveillance except deaths that are the result of trauma or accident.
- Is life-threatening (defined as a subject at immediate risk of death at the time of the event).
- Requires inpatient hospitalization or prolongation of existing hospitalization during the period of protocol-defined surveillance.
- Results in a persistent or significant disability/incapacity.
- Any other important medical event that may not result in death, be life threatening, or require hospitalization, may be considered an SAE when, based upon appropriate medical judgment, the event may jeopardize the subject and may require medical or surgical intervention to prevent one of the outcomes listed above. Examples of such medical events include allergic bronchospasm requiring intensive treatment in an emergency room or at home, blood dyscrasias or convulsions that do not result in inpatient hospitalization, or the development of drug dependency or drug abuse.

**Note\***

The SAEs should not be attributable to underlying disease for which the transplant was undertaken, or not attributable to GVHD, or not attributable to complications of immunosuppressive medications.

**g. Reporting Procedures:**

Adverse events including local and systemic reactions not meeting the criteria for SAEs will be captured on the appropriate case report form (CRF). Information to be collected for unsolicited adverse events includes event description, date of onset, investigator assessment of severity, investigator assessment of relationship to study product, date of resolution of the event, seriousness, and outcome. The severity of non-serious AEs will be assessed by a licensed clinician (i.e., medical doctor, nurse, nurse practitioner, physician's assistant). The relationship of non-serious AEs will be assessed by a licensed clinician (i.e., medical doctor, nurse practitioner, physician assistant) listed on the Form FDA 1572. All AEs occurring during the AE reporting period of the study will be documented appropriately regardless of relationship. AEs will be followed to adequate resolution or until considered stable.

Any medical condition that is present at screening will be considered a baseline condition and will not be reported as an AE. If the severity of any pre-existing medical condition increases during the study period, then it will be recorded as an AE.

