**7. Reporting Adverse Events:**

The investigator is responsible for reporting:

- Any Grade 3 Adverse event that is not attributable to underlying disease for which the transplant was undertaken, **or** not attributable to GVHD, **or** not attributable to complications of immunosuppressive medications that are observed or reported through 7 days following vaccination (Day 0 through Day 7), regardless of their relationship to study product.
- Any other AE will not be reported unless it meets the SAE criteria (see Section 16.f).

Initial vaccine reactions will be assessed for at least 15 minutes after vaccination. Subjects will be asked to record both solicited vaccine reactions and any unsolicited AEs on a memory aid for 7+ days after each vaccination (Day 0 through Day 7). Study personnel will attempt contacting the subjects by telephone and/or electronic communication at 1-3 days and 8-10 days after vaccination to review any AEs and SAEs. Adverse events and serious adverse events will be collected through 7 days following vaccination.

Solicited **systemic AEs** will be collected for 7+ days post each vaccination and will include the following: fevers, headache, fatigue/malaise, nausea, body ache/myalgia, general activity level, and vomiting. Solicited **injection site AEs** will include the following: pain, tenderness, redness/erythema, and swelling/induration at injection site.

**Reporting of Deviations:** All deviations will be reported to the IRB at the time of annual continuing review. Note: if the deviation affects patient safety and/or risk, the event will be reported immediately.

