**Visit 2: Days 28-42**

- Medical history
  - Inclusion/exclusion criteria will be checked- patients will be eligible to receive vaccine 2 if they received vaccine 1, regardless of GVHD status changes- but changes must be documented.
  - Concomitant medications will be recorded
- Targeted physical examination will be conducted including measurement of oral temperature (must be  $\leq 100.4^{\circ}\text{F}/38^{\circ}\text{C}$ ). If a physical exam is completed as a part of standard of care, another physical exam does not need to be completed. For females of childbearing age a pregnancy test will be performed.
- Approximately 20-40 mL of blood will be collected by venipuncture or from a central line prior to vaccination for HAI and MN assays to influenza virus antigens, phenotypic B, and T cell responses, B and T cell specific influenza responses, CBC d/p, quantitative CD4 $^{+}$ /CD8 $^{+}$ /CD19 $^{+}$  levels, and quantitative serum IgM and IgG concentrations.
- Study vaccine will be administered.

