## Methods and Timing for Assessing, Recording, and Analyzing Safety Parameters

### a. Adverse Events, Reactogenicity, Serious Adverse Events

The investigator is responsible for reporting:

- Any Grade 3 Adverse event that is not attributable to underlying disease for which the transplant was undertaken, **or** not attributable to GVHD, **or** not attributable to complications of immunosuppressive medications **and** are observed or reported through 7 days following vaccination, regardless of their relationship to study product.
- Any other AE will not be reported unless it meets the SAE criteria (see Section 16.f).

A physician, nurse, nurse practitioner, and/or physician's assistant will assess initial vaccine reactions for at least 15 minutes after vaccination. Subjects will be asked to record both solicited vaccine reactions

(reactogenicity) and any unsolicited AEs on a memory aid for 7+ days after each vaccination (Day 0 through Day 7). Study personnel will attempt to contact the subjects by telephone and/or electronic communication at 1 to 3 days and again 8-10 days after each vaccination to review any AEs and SAEs.

AEs and SAEs will be collected through 7 days following each vaccination. Adverse events will be followed until resolution or until considered stable. **Solicited injection site AEs** will include the following: pain, tenderness, erythema/redness, and swelling/induration (**Table 4**). **Solicited systemic AEs** will be collected for 7+ days post each vaccination and will include the following: fevers, fatigue/malaise, headache, nausea, body ache/myalgia, generally activity, and vomiting (**Table 5**).

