**d. Relationship to study products/vaccines:**

The investigator's assessment of the relationship of an AE to the study drug/vaccine is part of the documentation process, but it is not a factor in determining what is or is not reported in the study. If there is any doubt as to whether a clinical observation is an AE, the event should be reported. AEs must have their possible relationship to study vaccine assessed using the following terms: related or not related. In a clinical trial, the study product must always be suspect. To help assess, the following guidelines are used.

- **Related –** The event is temporally related to the administration of the study product and no other etiology explains the event.
- **Not Related –** The event is temporally independent of study product and/or the event appears to be explained by another etiology.

**Comparison of High vs. Standard Dose Flu Vaccine in Pediatric Stem Cell Transplant Recipients****DMID Protocol Number 16-0117****Protocol Version 8.0**

Date: 9/12/2019

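### Contradictory AE rules on GVHD: worsening is recorded regardless of relationship in one place and filtered by attribution in others, so AE/SAE data cannot support a reliable between-arm comparison

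*Protocol*

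**What the plan says.** Two sets of rules in the protocol govern which adverse events enter the data.

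**Inclusive rules.** Section 16.d says of the investigator's relationship assessment that "it is not a factor in determining what is or is not reported in the study". Section 16.g says "All AEs occurring during the AE reporting period of the study will be documented appropriately regardless of relationship" and, on conditions present at screening, "If the severity of any pre-existing medical condition increases during the study period, then it will be recorded as an AE". Neither section sets a grade limit.

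**Restrictive rules.** Sections 7 and 16.a make the investigator responsible for reporting "Any Grade 3 Adverse event that is not attributable to underlying disease for which the transplant was undertaken", with GVHD and complications of immunosuppressive medication added as further alternatives, through 7 days after vaccination. For the rest, 16.a says "Any other AE will not be reported unless it meets the SAE criteria (see Section 16.f"). The note to 16.f closes that second route with the same filter: "The SAEs should not be attributable to underlying disease for which the transplant was undertaken, or not attributable to GVHD", and then the immunosuppression alternative.

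**GVHD outside AE reporting.** Section 6 lists GVHD history and GVHD status among the data collected. At Visit 2 (section 14), a child who received dose 1 may receive dose 2 "regardless of GVHD status changes- but changes must be documented".

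**Analysis.** Protocol section 17.c plans descriptive summaries of solicited and unsolicited AEs by group. SAP section 6.1 covers solicited local and systemic AEs only.

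**The concern.** Children with stable GVHD are eligible, steroid treatment for GVHD enters the block randomization, and a change in GVHD status does not by itself prevent dose 2. A flare is therefore a foreseeable worsening of a pre-existing condition and a harm specific to this population. Of the earlier high-dose vaccine trials in protocol section B.4, the adult transplant trial enrolled recipients not on immunosuppression for active GVHD, so it does not cover children under treatment. The pediatric organ transplant trial did report rejection, the comparable event there, as a safety result.

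Hypothesis 2 asserts a similar safety profile. If attribution decides whether a flare is entered, and nine sites can read the filter differently, an absence of GVHD events in the by-arm tables cannot be taken as evidence of similarity. Independent review is affected too: section 16.h handles SAEs as 16.f defines them, so a site's attribution can keep an event from the independent safety monitor and the DSMB.

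**Working it through.** There is no plan figure to reproduce. The check sets the rules side by side.

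| Protocol section | Grade limit | Attribution filter |
|---|---|---|
| 16.d | none | relationship expressly not a filter |
| 16.g | none | documented whatever the relationship |
| 7 and 16.a | Grade 3, otherwise only SAEs | underlying disease, GVHD, immunosuppressive medication |
| 16.f note | serious events | the same three causes |
| 16.j halting rules | set rule by rule | relapse, GVHD, infection from the immunosuppressed state |

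1. **Attribution to GVHD is a relationship judgement.** Under 16.d an event that another etiology appears to explain is not related. An event attributed to GVHD is such an event. Filtering on that attribution is therefore filtering on relationship, which 16.d and 16.g say is not done. The section 7 sentence applies the filter and ends by saying that relationship does not matter.

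2. **Grade.** Section 16.g would record any worsening. Under 7 and 16.a, worsening below Grade 3 is not reported unless serious, whatever its cause.

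3. **The 'or' wording.** Each of three causes can be judged to apply or not, giving 2 × 2 × 2 = 8 attribution patterns.
   - Literal reading (not A, or not B, or not C): an event fails only if all three causes apply, so 1 of 8 patterns is excluded.
   - Probable intent (none of A, B, C): an event fails if any cause applies, so 7 of 8 are excluded.
   - The readings disagree on 7 − 1 = 6 of 8 patterns, including attribution to GVHD alone.

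   These are counts of patterns, not of expected events.

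4. **One event followed through.** Take a Grade 3 flare within Day 0–7, attributed to GVHD alone. Section 16.g records it. Sections 7 and 16.a report it on the literal reading and omit it on the intended one. If the child is admitted, the 16.f note splits in the same way.

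5. **Other capture.** After dose 1, the Visit 2 instruction applies. After dose 2, the Visit 3 list has AEs through 7 days, concomitant medication and an examination if indicated. The Visit 4 list has blood samples and a nasal swab. Neither mentions GVHD changes. Section 6 gives no time points for GVHD status.

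6. **Analysis.** In the SAP, GVHD is a randomization stratum component (1.1.4), a baseline descriptor (4), an effect modifier of HAI response (5.4) and a possible predictor of influenza (7.3). It is nowhere a safety outcome.

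**The case against.** The best defence is that the protocol means to record everything and report some of it. Section 16.g speaks of capturing, documenting and recording; sections 7 and 16.a speak of reporting. The memory aid takes unsolicited events without a cause limit, and section 17.c summarises severities of unsolicited AEs, which would mean little if only Grade 3 events were kept. This reading is possible, so it is not established that any event was lost. But the protocol never states it, and it does not rescue 16.d, which speaks of what is reported.

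A reader might go further and infer that GVHD worsening cannot be compared between arms at all. The documents do not support that: GVHD status is collected and changes must be documented at Visit 2, which allows a randomized comparison after dose 1.

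Nor is the stated safety aim undermined. Aim 2 and the primary safety analysis in 17.c concern solicited events, so a GVHD summary is an addition. No document says how a blinded investigator would attribute a flare, and 16.d says the study product must always be suspect.

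Finally, version 8.0 is dated 9/12/2019, after the 2016–2017 to 2018–2019 enrollment seasons of the main cohort. Rewording cannot recover that cohort's Day 0–7 events. This limits what a protocol change can achieve, but not what the SAP can add.

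**Conclusion.** The contradiction stands on the text. Sections 16.d and 16.g cannot both be followed with sections 7, 16.a and the 16.f note, and the filter can be applied in opposite ways to an event attributed to GVHD alone. GVHD worsening therefore cannot be compared reliably between arms from AE/SAE data. The gap is widest after dose 2, and the SAP leaves the Visit 2 information unused for safety.

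The size is qualitative. The documents give no rate of GVHD worsening and do not show how sites applied the filter, so no number of missing events can be stated. The conclusion that flares are omitted rests on the probable rather than the literal reading of the filter. The conclusion that the rules conflict and permit inconsistent capture does not. The immunogenicity results and solicited-event comparisons are unaffected. The change is worth making, mainly for the by-arm GVHD summary.

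**What to change.** 1. **SAP section 6.** Add a descriptive by-arm summary of new or worse GVHD from Visit 1 to Visit 2, using the changes that the Visit 2 procedures already require to be documented. This needs no new data and remains possible for the cohort enrolled in 2016–2019.

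2. **One capture rule.** Reconcile protocol sections 7, 16.a, 16.d, the 16.f note and 16.g. Record every Grade 3 AE and every SAE in the existing Day 0–7 windows, with attribution as a data field, and give the sentence on pre-existing conditions the same threshold. Show by-arm counts with and without events attributed to disease, GVHD or immunosuppression. This makes the unsolicited-event summary in 17.c interpretable.

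3. **Any filter kept for expedited reporting.** Word it so that only one reading is possible. Check it against the halting-rule exclusion in 16.j, which names different causes. Halting rule 1 depends on what counts as an SAE, so a change to the 16.f note could affect it, and the two passages must be reconciled.

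**Cost.** Item 1 is SAP text and one table. Item 2 adds event forms within two Day 0–7 windows per season. If the SAE note changes, it also adds 24-hour SAE notifications, safety monitor and IRB review, and follow-up through resolution. Rewording under version 8.0 reaches only events still to be collected.

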## **h. Serious Adverse Event Detection and Reporting**

SAEs as defined in Section 16.f will be:

- Notified to the IND Sponsor/Lead PI ([name]), local site PI and/or Sub-Is and DMID Pharmacovigilance Group (PVG) within 24 hours of knowledge of the SAE.
- Assessed for severity and relationship by a licensed clinician listed on the FDA Form 1572 as the PI or a Sub-Investigator.
- Recorded on the appropriate SAE report form.
- Followed through resolution by a study physician.
- Reviewed by an Independent Safety Monitor (ISM), Data and Safety Monitoring Board (DSMB) (periodic review unless related), DMID, and IRB.
- SAEs related to the study vaccine that are unexpected and fatal or life-threatening will be reported to the FDA no later than 7 calendar days after SAE awareness.
- SAEs related to the study vaccine that are unexpected and serious (not fatal or life-threatening) are to be reported to the FDA no later than 15 calendar days after SAE awareness.
- All other SAEs will be submitted with the FDA Annual Report in summary form.
- All SAEs unexpected and deemed related to the study vaccine will be reported to Sanofi within 7-15 calendar days after SAE awareness.

SAEs occurring through 7 days following vaccination will also be reported to the local IRB within 1-2 calendar days as the team becomes aware of the SAE or per local IRB protocol/procedures.

Any AE that meets a protocol-defined serious criterion as defined in Section 16.f will be submitted immediately (within 24 hours of site awareness) on a SAE form to the DMID Pharmacovigilance Group, to the following address:

### **i. Independent Safety Monitor (ISM) and the Data Safety Monitoring Board (DSMB):**

An Independent Safety Monitor (ISM) is a physician at the enrollment site with relevant expertise whose primary responsibility is to provide independent medical assessment in a timely fashion at each site. Each site will have an ISM and back-up ISM. Participation is for the duration of the study.

The ISM should be able to readily access participant records in real time, have the privileges to examine the subject, and provide an independent medical assessment and recommendation to the IND sponsor and DMID. The primary focus of the ISM is to independently review all SAEs with follow-up through resolution and thoroughly investigate those events considered unexpected. Clinical and laboratory data, clinical records, and other study-related records should be made available for ISM review. The ISM may be a faculty member at the clinical site but will not be under the direct supervision of the PI. It is the responsibility of the PI to ensure that the ISM is apprised of all new safety information relevant to the study product and the study.

Safety oversight will be conducted by a Data Safety and Monitoring Board (DSMB) that is an independent group with expertise to interpret data from this study and will monitor subject safety and advise DMID and the IND sponsor. The DSMB members will be separate and independent of study personnel participating in this study and should not have scientific, financial, or other conflict of interest related to this study. The committee will consist of a minimum of 3 members. A simple majority will be considered a quorum for meeting purposes.

The DSMB will operate under the rules of a DMID-approved charter that will be written at the organizational meeting of the DSMB and defines the data elements to be assessed and the procedures for data reviews. At this time, each data element that the DSMB needs to assess will be clearly defined. Procedures for DSMB reviews/meetings will be defined in the charter. The DSMB will review applicable data to include, but not limited to, overall study progress and participant, clinical, safety, reactogenicity, and immunogenicity data. Reports may include enrollment and demographic information, medical history, concomitant medications, physical assessments, clinical laboratory values, dosing compliance, and solicited and unsolicited AE/SAEs. Additional data may be requested by the DSMB, and interim statistical reports may be generated as deemed necessary and appropriate by the IND sponsor and DMID. The DSMB may receive data in aggregate and presented by treatment arm. The DSMB may also be provided with expected and observed rates of the expected AEs in an unblinded fashion, and may request the treatment assignment be unblinded for an individual subject if required for safety assessment. The DSMB will review grouped and unblinded data in the closed session only. The DSMB will meet and review this data at scheduled time points or ad hoc as needed during this study as defined in the DSMB charter. As an outcome of each review/meeting, the DSMB will make a recommendation to the IND sponsor and DMID as to the advisability of proceeding with study vaccinations (as applicable), and to continue, modify, or terminate this trial.

DMID or the DSMB chair may convene the DSMB on an ad hoc basis according to protocol criteria or if there are immediate concerns regarding observations during the course of this trial. The DMID Medical Monitor is empowered to stop enrollment and study vaccinations if adverse events that meet the halting criteria are reported. The DMID Medical Monitor and the ISM will be responsible for reviewing SAEs in real time. The DSMB will review SAEs on a regular basis and ad hoc during this study.

The DSMB will review study progress and participant, clinical, safety, reactogenicity, and immunogenicity data at the following times:

- Data review for safety and reactogenicity at specified times during the course of this trial – every 6 months, starting after the first patient is enrolled until the end of the study.
- Final review – 6 to 8 months after clinical database lock to review the cumulative unblinded safety, reactogenicity, and immunogenicity data for this study. The data will be provided in a standard

